Spirometry	X	Spirometry will be performed post-bronchodilator and according to the American Thoracic Society Guidelines/European Respiratory Society Guidelines. If spirometry cannot be performed, historical post-bronchodilator ppFEV ₁ results within 1 year before screening can be used to determine eligibility. Section 8.2 exclusion criterion #7 and Section 11.5.5 .
Urine cotinine	X	Section 11.5.2
AEs and SAEs	Continuous from signing of ICF through last Safety Follow-up Visit	Section 11.5.1
Medications review	Continuous from signing of ICF through last Safety Follow-up Visit	Section 9.6

AAT: alpha-1 antitrypsin; Ab: antibody; AE: adverse event; β -hCG: beta-human chorionic gonadotropin; FSH: follicle-stimulating hormone; HBsAg: hepatitis B surface antigen; HCV: hepatitis C virus; HIV-1/HIV-2 Abs: antibodies against human immunodeficiency viruses 1 and 2; ICF: informed consent form; ppFEV₁: percent predicted forced expiratory volume in 1 second; SAE: serious adverse event

Notes: Screening procedures (including informed consent) can be performed over more than 1 day. Informed consent must be obtained prior to any procedures. Repeat Screening assessments and Screening assessments that were not conducted at the initial visit during the Screening Period may be performed at the clinic or at home by a qualified visiting nurse, if permitted by ethical and regulatory authorities and agreed upon after investigator and subject consultation. If a second blood sample is required >42 days after the last dose of augmentation therapy to measure antigenic AAT levels to confirm eligibility, this second blood sample (and the second functional AAT level drawn at the same time) can be drawn at a home visit or clinic visit.

Table 3-3 Study VX19-864-101: Treatment Period and Follow-up Visits

Event/ Assessment	Treatment Period						VX-864 Washout Visit 7 (±2) Days After Last Dose of Study Drug	ETT Visit ^e	Safety Follow-up Visit 14 (±2) Days After Last Dose of Study Drug	Safety Follow-up Visit 28 (±2) Days After Last Dose of Study Drug	Comments
	Day 1 ^a	Day 7 (±1) ^b	Day 14 (±2) ^b	Day 21 (±2) ^b	Day 28 (-2) ^c						
Inclusion and exclusion criteria confirmation	X										

- ^a **On Day 1, all assessments must be completed before the first dose of study drug except for the post dose PK sampling, which is done at 3, 5, and 8 hours (±30 minutes) after dosing in the clinic.**

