9 STATISTICAL ANALYSIS

9.1 General Considerations

The Schedule of Assessments is provided in Section 3 of the CSP. The precision standards for reporting safety variables are provided in an internal Biometrics document that specifies programming rules including the precision for derived variables.

Continuous variables will be summarized using the following descriptive summary statistics: the number of subjects (n), mean, SD, median, minimum value (min), and maximum value (max).

Categorical variables will be summarized using counts and percentages.

Baseline value, unless specified otherwise, will be defined as the most recent non-missing measurement (scheduled or unscheduled) collected before the first dose of study drug. For

ECGs, the baseline value will be defined as the average of the non-missing pre-dose measurements (triplicate) collected before the first dose of study drug. For subjects who have ever been on augmentation therapy at any time, only functional and antigenic AAT levels collected >42 days after the last dose of augmentation therapy can be used to define baseline values. For antigenic AAT levels, only the screening results obtained from the on-treatment assay can be used to define baseline values if the Day 1 pre-dose results are missing.

Change (absolute change) from baseline will be calculated as post-baseline value – baseline value.

Relative change from baseline will be calculated and expressed in a percentage as $100\% \times (\text{post-baseline value} - \text{baseline value})$ /baseline value.

Treatment-emergent (TE) Period will include the time period starting from the date of the first dose of study drug to either (1) Safety Follow-up Visit 28 days after the last dose of study drug, (2) Early Termination of Treatment (ETT) Visit if it replaces the Safety Follow-up Visit 28 days after the last dose of study drug, or (3) 28 days after the last dose date for subjects who do not have a Safety Follow-up Visit 28 days after the last dose or an equivalent ETT.

Unscheduled visits: Data obtained from unscheduled visits will be included in the analysis as follows:

- In scheduled visit windows per specified visit windowing rules
- In the derivation of baseline and last on-treatment measurements
- In the derivation of maximum and minimum values during the TE period, and maximum and minimum change from baseline values during the TE period for safety analyses
- In individual subject data listings as appropriate

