9.4.1 Adverse Events

AEs will be coded using MedDRA. The number and percentage of subjects experiencing an AE will be summarized by the MedDRA SOC and PT. AEs will be classified as pretreatment or treatment-emergent as follows:

Pretreatment AEs: AEs that occurred before the first dose of study drug

Treatment-emergent AEs: AEs that worsened or started on or after the first dose date of study drug through the end of the TE Period

Post-treatment AEs: AEs that worsened or started after the TE Period

For AEs with completely missing or partial start dates, if there is no clear evidence that the AEs started before or after the first dose of study drug, the AEs will be classified as TEAEs.

Imputation rules for missing or partial AE start dates are defined as Appendix C.

AE summary tables will be presented for only TEAEs by treatment group (including placebo and each VX-864 dose group) and overall across the VX-864 treatment groups, and will include the following:

- Overview of TEAEs
- All TEAEs
- TEAEs by strongest relationship
- TEAEs by maximum severity
- TEAEs leading to death
- Serious TEAEs
- Related TEAEs
- TEAEs leading to treatment discontinuation
- TEAEs leading to treatment interruption

When summarizing the number and percentage of subjects with an event, subjects with multiple occurrences of the same AE or a continuing AE will be counted once. Only the maximum severity level will be presented in the severity summaries, and the strongest relationship level in the relationship summaries.

In addition, listings containing individual subject-level AE data for all deaths, SAEs, treatment discontinuations, and treatment interruptions will be provided separately.

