9.4.3 Electrocardiogram

For the treatment-emergent ECG measurements, a summary of observed values and change from baseline values will be provided by treatment group at each visit and time point, as applicable, for the following ECG measurements: RR interval (msec), PR interval (msec), QT interval (msec), QTcF interval (msec), QRS duration (msec), and heart rate (beats per minute).

The number and percentage of subjects meeting threshold analysis criteria during the TE Period will be summarized by treatment group.

Since ECGs are performed in triplicate, the mean of the ECGs will be used as the ECG value for summaries of observed values and change from baseline values, and all reported ECGs will be used to conduct threshold analyses.

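### The treatment-emergent period starts on the calendar date of the first dose, so Day 1 predose laboratory, ECG and vital-sign values are baseline and can also enter the treatment-emergent threshold counts

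*SAP*

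**What the plan says.** SAP 9.1 defines the treatment-emergent (TE) Period by calendar date: "Treatment-emergent (TE) Period will include the time period starting from the date of the first dose of study drug to either" one of three end points. Protocol 12.3.1 uses the same start and applies the TE Period to safety analyses by default. SAP 10.1.1 repeats it for the interim analysis.

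Baseline in SAP 9.1 is tied to the dose: it is the "most recent non-missing measurement (scheduled or unscheduled) collected before the first dose of study drug". The ECG rule in that section is dose-based too: it averages the triplicate readings available ahead of dosing.

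Protocol Table 3-3, footnote a, fixes the order of events on Day 1: "On Day 1, all assessments must be completed before the first dose of study drug except for the post dose PK sampling". The ECG row of that table adds a second Day 1 triplicate 6 hours after dosing.

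The TE Period is the window for threshold counts of laboratory values (SAP 9.4.2), ECGs (9.4.3) and vital signs (9.4.4). For ECGs the SAP adds that "all reported ECGs will be used to conduct threshold analyses". SAP 9.1 also mentions maxima and minima over the TE Period, in its rule on unscheduled visits.

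For adverse events, SAP 9.4.1 has the same two kinds of boundary. One category is set by the dose: "Pretreatment AEs: AEs that occurred before the first dose of study drug". The other is set by the date: "Treatment-emergent AEs: AEs that worsened or started on or after the first dose date of study drug through the end of the TE Period".

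**The concern.** One boundary is set by the dose and the other by the date. A value taken on Day 1 before dosing precedes the dose but carries its date, so it falls on both sides. This is the scheduled case, not an exception, because footnote a requires it.

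Safety is a primary objective, and the threshold tables are where liver-test and QTcF abnormalities are counted. If the written rule is programmed literally, a subject whose only value beyond a limit was recorded before any study drug appears as a treatment-emergent case. Arms are small (8, 8, 8 and 16 subjects), so one such subject moves a percentage by 1/8 = 12.5 points or 1/16 = 6.25 points.

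**Working it through.** **Step 1: which rule a Day 1 predose value meets.**

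| Rule | Boundary | Day 1 predose value |
|---|---|---|
| Baseline (SAP 9.1) | before the first dose | qualifies |
| TE Period (SAP 9.1, SAP 10.1.1, protocol 12.3.1) | from the date of first dose | qualifies |
| Pretreatment AE (SAP 9.4.1) | before the first dose | an AE starting then qualifies |
| TEAE (SAP 9.4.1) | on or after the first dose date | the same AE qualifies |

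No visible text removes predose values from the TE window. For ECGs, a date alone cannot separate the predose triplicate from the 6-hour triplicate.

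**Step 2: how much of the window is predose.** Scheduled time points from Table 3-3 for a subject who completes all visits (no Early Termination Visit):

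| Assessment | Postdose time points | Postdose | Date-based TE |
|---|---|---|---|
| Chemistry, hematology, coagulation | Days 7, 14, 21, 28, washout, two follow-ups | 7 | 8 |
| Vital signs | Days 7, 14, 28, two follow-ups | 5 | 6 |
| ECG triplicates | Day 1 at 6 h, Days 7, 28, two follow-ups | 5 (15 readings) | 6 (18 readings) |

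So the predose share is 1 of 8, 1 of 6, and 3 of 18.

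**Step 3: illustrative size.** The documents give no rate p at which a value crosses a limit, so p is assumed. With independent time points, the chance of at least one flag is 1 − (1 − p)^n.

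| p | Laboratory, n = 7 → 8 | ECG or vital signs, n = 5 → 6 |
|---|---|---|
| 1% | 6.8% → 7.7% | 4.9% → 5.9% |
| 2% | 13.2% → 14.9% | 9.6% → 11.4% |
| 5% | 30.2% → 33.7% | 22.6% → 26.5% |

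For example, 1 − 0.99^7 = 6.8% and 1 − 0.99^8 = 7.7%.

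Repeated values in one person are correlated, which shrinks the increase. I simulated 400,000 subjects with equally correlated normal values (correlation 0.6 or 0.8, assumed), 7 versus 8 laboratory values and no drug effect. The share flagged rises by 0.2 to 0.4 points at p = 1% and by 1.0 to 1.8 points at p = 10%. At 1.8 points that is 8 × 0.018 = 0.14 expected extra subjects in an arm of 8, and 16 × 0.018 = 0.29 in the arm of 16.

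**The case against.** The best reply is that the deciding rules may exist but not be public. SAP 9.1 refers to visit-windowing rules, and SAP 9.4.2 to 9.4.4 to threshold criteria, that are not in the available text. Either could exclude predose values. ECGs carry a time-point label, and SAP 9.4.3 summarises them by visit and time point, so a programmer can separate them without relying on the date. This stands as a limit: the visible definition does not exclude predose values, but one cannot say that the programs will include them.

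Much of the safety output is also protected. Change uses a post-baseline value, so visit-level change summaries are sound. Pulse oximetry has no threshold table. No visible section specifies a table of maxima or minima. The rule is the same in every arm, and safety is descriptive without testing.

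The adverse-event overlap has little reach. The protocol's list of AE data (13.1.1.3) has a date of first occurrence and no time, and SAP 9.4.1 already defaults to TEAE when a missing or partial start date leaves the order unclear.

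A reader might infer something stronger: that the rule masks a drug benefit, because a subject abnormal before dosing who normalises on drug is still counted. With an assumed 1 SD fall in the analyte and 10% of untreated values above the limit, the same simulation moves from 4–5% to 11–12% flagged, so more than half of the cases would be predose. The documents do not support those inputs. The liver benefit in protocol 5.1 is a lower risk of progressive disease, not an enzyme fall within 28 days, and exclusion criteria 11 and 12 remove clinically evident liver disease and larger laboratory abnormalities at screening. The threshold shift from baseline and the by-visit summaries in SAP 9.4.2 would also show such a subject.

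**Conclusion.** The point holds as a definitional error in the visible text. Day 1 predose laboratory, ECG and vital-sign values are both baseline and inside the TE Period, and can enter the threshold counts and any TE-period maxima or minima. It applies to subjects who have a Day 1 predose value. Where that is missing, baseline comes from an earlier measurement and nothing overlaps, so it would be too strong to say that every subject is affected.

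The counts of 1 in 8, 1 in 6 and 3 in 18 follow directly from Table 3-3. The effect on reported percentages does not: it depends on assumed flag rates and correlations and is probably small. Efficacy analyses are untouched. This is a minor correction, worth making because it concerns a primary objective and is easy to settle.

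**What to change.** 1. In SAP 9.1, SAP 10.1.1 and protocol 12.3.1, state that for laboratory, ECG and vital-sign measurements the TE Period begins after the first dose. Decide this by collection time, or for ECGs by the predose/postdose time-point label.
2. In the same places, state that Day 1 predose values are baseline only and do not enter TE threshold counts, maxima or minima.
3. In SAP 9.4.1, add a tie rule so that the two AE categories do not overlap: an AE starting on Day 1 is a TEAE unless there is clear evidence that it began before the first dose.

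The cost is a few sentences and a time or label comparison in the programs. No new data are required for ECGs, and Day 1 AEs of unknown timing remain TEAEs. If the unpublished rules already do this, the change only records existing practice.

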9.2 Background Characteristics

9.2.1 Subject Disposition

The disposition summary will be provided by treatment group and overall.

The number of subjects, based on the All Subjects Set, in the following disposition categories, will be summarized:

- All Subjects Set
- Full Analysis Set
- Safety Set
- Randomized
- Randomized but not dosed

The number and percentage of subjects, based on the FAS, in each of the following disposition categories, will be summarized:

- Completed treatment
- Discontinued treatment and the reason for discontinuation from treatment
- Completed study
- Discontinued study and the reason for discontinuation from study

9.2.2 Demographics and Baseline Characteristics

Demographics and baseline characteristics will be summarized based on the FAS by treatment group and overall.

Demographic data will include the following:

- Age (in years)
- Sex (female and male)
- Ethnicity (Hispanic or Latino, not Hispanic or Latino, and not collected per local regulations)

• Race (White, Black or African American, Asian, American Indian or Alaska Native, Native Hawaiian or Other Pacific Islander, Other, and Not Collected per Local Regulations)

Baseline characteristics will include the following:

- Weight (kg)
- Height (cm)
- BMI (kg/m^2)
- Prior Augmentation Therapy (Yes, No)
- Smoking History (Yes, No)
- ppFEV₁ category determined during the Screening Period or from historical data (< 50%, ≥50%)
- ppFEV₁ obtained during the Screening Period or from historical data (%)
- FEV₁ obtained during the Screening Period or from historical data (L)
- FVC obtained during the Screening Period or from historical data (L)
- Ratio of FEV₁ and FVC obtained during the Screening Period or from historical data (%)
- Functional AAT level (μM)
- Antigenic AAT level (μM)

9.2.3 Medical History

Medical history will be coded by using the Medical Dictionary for Regulatory Activities (MedDRA). Medical history will be summarized descriptively based on the FAS by MedDRA system organ class (SOC) and preferred term (PT). This summary will be provided by treatment group and overall.

9.2.4 Prior and Concomitant Medications

Medications will be coded using the World Health Organization-Drug Dictionary (WHODrug) and categorized as the following for the purposes of analysis:

Prior medication: Medication that started before the first dose of study drug

Concomitant medication: Medication continued or newly received during the TE Period

Post-treatment medication: Medication continued or newly received after the TE Period

A given medication may be classified as a prior medication, a concomitant medication, a post-treatment medication, or more than one of these categories.

Vertex Pharmaceuticals Incorporated

If a medication start date is on or after the first dose date of study drug, then the medication will be classified as a concomitant medication regardless of whether the medication end date is missing or not. If a medication end date is before the first dose date of study drug, then the medication will be classified as a prior medication regardless of whether the medication start date is missing or not. Note that a medication that started before the first dose of study drug and continued after the first dose will be classified as a prior medication and separately as a concomitant medication.

If a medication has a missing or partially missing start/end date and it cannot be determined whether it was taken before the first dose of study drug, or concomitantly, it will be classified as a prior and a concomitant medication.

Missing or partial dates will be imputed for medications. Details for imputing missing or partial start and/or stop dates of medications are described in Appendix B.

Prior and post-treatment medications will not be summarized but will only be listed. Concomitant medications will be summarized based on the FAS by PT. This summary will be provided by treatment group and overall across the VX-864 treatment groups. Bronchodilator usage will also be listed.

Prior, concomitant, and post-treatment non-pharmacological therapy will be listed.

9.2.5 Study Drug Exposure and Compliance

Study drug exposure (in days) will be calculated as (last date of dosing – first date of dosing) + 1, regardless of study drug interruption, and will be summarized descriptively based on the Safety Set by treatment group and overall. It will also be summarized in categories: ≤ 7 days, > 7 to ≤ 14 days, > 14 to ≤ 21 days, > 21 to ≤ 28 days, and > 28 days, using counts and percentages.

Study drug compliance will be calculated as $100 \times [1 - (\text{total number of days of study drug interruption}) / (duration of study drug exposure in days)]. A study drug interruption on a given day is defined as any interruption of the study drug on that day. A study drug interruption that continues through the end of study participation (i.e., subject does not resume study drug before the end of study participation) will not be included in the compliance calculation. Study drug compliance will be summarized descriptively based on the FAS by treatment group and overall. It will also be summarized in categories: <math><80\%$ and $\ge80\%$, using counts and percentages.

9.2.6 Important Protocol Deviations

An important protocol deviation (IPD) is a deviation that may significantly affect the completeness, accuracy, or reliability of the study data or that may significantly affect a subject's

rights, safety, or well-being. IPD rules will be developed and finalized before clinical database lock. IPDs will be identified by the PD review team according to the Protocol Deviation Plan.

IPDs will be summarized descriptively based on the FAS by treatment group and overall.

9.3 Efficacy Analysis

All efficacy analyses described in this section will be based on the FAS, unless otherwise specified. Subjects will be analyzed according to the treatment to which they were randomized.

9.3.1 Analysis of Primary Efficacy Variable

9.3.1.1 Definition of Primary Efficacy Variable

The primary efficacy variable is the change from baseline in plasma functional AAT levels at Day 28.

9.3.1.2 Primary Analysis

The primary analysis of the primary efficacy variable includes data from VX-864 treatment groups and the placebo group. The primary comparison consists of the pairwise comparison between each dose of VX-864 and placebo.

The primary analysis will be based on a mixed-effects model for repeated measures (MMRM) with change from baseline at Days 7, 14, and 28 as the dependent variable. The MMRM model will include the treatment group, visit, and treatment-by-visit interaction as fixed effects. An unstructured covariance structure will be used to model the within-subject errors. If the model estimation does not converge, a compound symmetry covariance structure will be used instead. The model will be estimated using restricted maximum likelihood. Denominator degrees of freedom for the F-test for fixed effects will be estimated using the Kenward-Roger approximation. Conditional on the observed data and covariates, missing data will be assumed to be missing at random; consequently, no imputation of missing data will be performed.

The primary result obtained from the model will be the estimated treatment difference between each VX-864 treatment group in the model and the placebo group at Day 28. The adjusted means with 2-sided 95% confidence intervals and 2-sided *P* values will be provided. In addition, the estimated treatment differences, obtained from the model, between each VX-864 treatment group

in the model and the placebo group at each post-baseline visit will be provided, along with 2-sided 95% confidence intervals and 2-sided *P* values.

The observed values and change from baseline of functional AAT levels will also be summarized descriptively by treatment group at each visit.

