9.3 Method of Assigning Subjects to Treatment Groups

Approximately 40 subjects in total will be randomized to receive VX-864 or placebo 2:1:1:1 to VX-864 500 mg every 12 hours (q12h), VX-864 300 mg q12h, VX-864 100 mg Q12h, or placebo.

Of these, approximately 20 subjects will be randomized 2:2:1 to VX-864 500 mg q12h, VX-864 300 mg q12h, or placebo first. The remaining subjects (approximately 20) will be randomized 2:2:1 to VX-864 500 mg q12h, VX-864 100 mg q12h, or placebo.

Each randomized subject will be assigned a unique subject number. Randomization will be stratified by post-bronchodilator ppFEV₁ obtained either during the Screening Period or from a post-bronchodilator historical ppFEV₁ value measured within 1 year before screening (<50% versus ≥50%).

An interactive web or voice response system (IWRS) will be used to assign subjects to treatment. The randomization code will be produced by Vertex Biostatistics or a qualified randomization vendor. The Vertex study biostatistician will review and approve the production of the final randomization list, which will be reviewed and approved by a designated unblinded biostatistician who is not a member of the study execution team (SET).

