12.3.2 Demographics and Background Characteristics

Subject disposition (e.g., completed treatment, prematurely discontinued the treatment and the reason for discontinuation) will be summarized by treatment group.

Demographic and other baseline characteristics (e.g., plasma AAT levels and ppFEV₁) will be summarized by treatment group. No statistical tests will be carried out to evaluate baseline imbalances between treatment groups.

Medications used will be coded using the World Health Organization-Drug Dictionary (WHODrug) and summarized descriptively. Exposure to study drug (i.e., duration of treatment) and dosing compliance (i.e., percentage of days being compliant to treatment) will be summarized descriptively.

Important protocol deviations will be provided in an individual subject data listing, and summarized, as appropriate.

Additional details will be provided in the SAP.

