12.3.3 Efficacy Analysis

12.3.3.1 Analysis of the Primary Variable

The primary endpoint to assess efficacy is the change from baseline in plasma functional AAT levels at Day 28. This primary analysis will be based on a mixed-effects model for repeated

measures (MMRM) with change from baseline at Days 7, 14, and 28 as the dependent variable. The model will include treatment group, visit, and treatment-by-visit interaction as fixed effects. The model will be estimated using restricted maximum likelihood. Denominator degrees of freedom for the F -test for fixed effects will be estimated using the Kenward-Roger approximation. An unstructured covariance structure will be used to model the within-subject errors. If the model estimation does not converge, a compound symmetry covariance structure will be used instead.

[REDACTED]

Details will be provided in the SAP.

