7 STUDY DESIGN

7.1 Overall Design

This is a Phase 2, randomized, double-blind, placebo-controlled study of VX-864. Schematics of the study design are shown in Figure 7-1 and Figure 7-2.

Approximately 40 subjects in total with the PiZZ genotype and antigenic AAT levels <8 μ M at screening will be randomized to VX-864 or placebo 2:1:1:1 to VX-864 500 mg q12h, VX-864 300 mg q12h, VX-864 100 mg q12h, or placebo.

[figure not shown]
Of these, approximately 20 subjects will be randomized 2:2:1 to VX-864 500 mg q12h, VX-864 300 mg q12h, or placebo first. The remaining subjects (approximately 20) will be randomized

Vertex Pharmaceuticals Incorporated

2:2:1 to VX-864 500 mg q12h, VX-864 100 mg q12h, or placebo. Randomization will be stratified by post-bronchodilator percent predicted forced expiratory volume in 1 second (ppFEV₁) obtained either during the Screening Period or from a historical post-bronchodilator ppFEV₁ value measured within 1 year before screening (<50% versus $\ge50\%$).

Screening assessments for subjects who have never been on augmentation therapy are listed in Table 3-1 of the protocol. Screening assessments for subjects who have been on augmentation therapy at any time are listed in Table 3-2 of the protocol. Treatment Period assessments for all subjects are listed in Table 3-3 of the protocol.

[figure not shown]
Figure 7-1 Schematics of Study Design for Subjects Who Have Never Been on Augmentation Therapy

AAT: alpha-1 antitrypsin; N: number of subjects; q12h: every 12 hours

Notes: Figure is not drawn to scale. Subject numbers include subjects who have never been on augmentation therapy and subjects who have been on augmentation therapy at any time. Antigenic AAT levels must be drawn to confirm eligibility and sent to the central laboratory; results must be obtained and confirmed to be <8 µM before randomization. Once antigenic AAT levels have been confirmed to meet this eligibility criterion, randomization and Day 1 can occur any time within the remaining screening window. Sites should allow at least 14 days for sample processing and antigenic AAT level result reporting.

Figure 7-2 Schematics of Study Design for Subjects Who Have Been on Augmentation Therapy at Any Time

AAT: alpha-1 antitrypsin; N: number of subjects; q12h: every 12 hours

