9.3.2.2 Analysis Method

The analysis of the secondary efficacy variable includes data from VX-864 treatment groups and the placebo group.

Analysis of the secondary efficacy variable will be based on an MMRM similar to the primary analysis of the primary efficacy variable, with change from baseline in plasma antigenic AAT levels at Days 7, 14, 28 as the dependent variables and the treatment group, visit, and treatment-by-visit interaction as fixed effects. The adjusted means and the estimated treatment differences obtained from the model between each VX-864 treatment group in the model and the placebo group at Day 28, as well as at each post-baseline visit, will be provided, with 2-sided 95% confidence intervals and 2-sided *P* values.

The observed values and change from baseline of the antigenic AAT levels will be summarized descriptively by treatment group at each visit.

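### The primary and secondary MMRMs omit baseline AAT and the ppFEV₁ randomisation stratum: a possible loss of precision that is cheap to repair, not an error

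*SAP*

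**What the plan says.** - **Primary model.** SAP 9.3.1.2: "The MMRM model will include the treatment group, visit, and treatment-by-visit interaction as fixed effects". Protocol 12.3.3.1 agrees: "The model will include treatment group, visit, and treatment-by-visit interaction as fixed effects". The outcome is change in functional AAT at Days 7, 14 and 28, and the primary result is each dose–placebo difference at Day 28.
- **Secondary model.** SAP 9.3.2.2 repeats the structure for antigenic AAT: "and the treatment group, visit, and treatment-by-visit interaction as fixed effects".
- **Randomisation.** Protocol 9.3: "Randomization will be stratified by post-bronchodilator" ppFEV₁, below 50% versus 50% or above. SAP 7.1 says the same. About 20 subjects are first randomised 2:2:1 to 500 mg, 300 mg or placebo; the remaining 20 or so go 2:2:1 to 500 mg, 100 mg or placebo.
- **Baseline.** SAP 9.1: the value "will be defined as the most recent non-missing measurement (scheduled or unscheduled) collected before the first dose of study drug", that is, a single measurement.
- **Availability.** SAP 9.2.2 already summarises functional and antigenic AAT at baseline and the ppFEV₁ "category determined during the Screening Period or from historical data".
- **Missing data.** SAP 9.3.1.2 and protocol 12.3.3.3 assume missing at random given the observed data and covariates (the protocol has the singular). The stated model contains no covariate.

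**The concern.** Analysing change without a baseline term fixes the slope of the Day 28 level on baseline at 1. Assay error and within-subject variation in a single baseline measurement pull the true slope below 1; a drug effect that grows with baseline pushes it above 1. The planned model estimates neither. The randomisation also uses a stratum that the model ignores.

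What is at stake is the precision of the dose–placebo contrasts in a study where three of the four arms have 8 subjects. A secondary matter is that the missing-at-random assumption refers to covariates that do not exist, so missingness that depends on baseline is only partly covered, through the observed change scores.

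**Working it through.** **1. The plan's own figures.** 40 split 2:1:1:1 gives 16/8/8/8; two parts of 20 at 2:2:1 give 8+8, 8, 8 and 4+4. These agree with SAP 7.2. The precision behind the sample size cannot be reproduced, because no SD or half-width is visible. With 10% missing, 36 subjects remain at Day 28, and 36 − 4 arms = 32 degrees of freedom.

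**2. Cost of terms that carry no information.** For q such covariates the width ratio is [t(0.975, df − q)/t(0.975, df)] × √(1 + q/(df − q − 1)). With df = 32 and q = 1: 1.0013 × 1.0165 = 1.018. Simulation with blocks of 5 within stratum (block size assumed) gives 1.004–1.006 for the stratum alone and 1.023–1.025 for both terms.

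**3. Gain with a slope common to all arms.** Let R be the Day 28 SD divided by the baseline SD, and r their correlation; both are assumptions. In baseline-SD units the change score has variance 1 + R² − 2rR, and the adjusted residual has R²(1 − r²). With both terms added and the stratum not prognostic, the width ratio is about 1.025·R√(1 − r²)/√(1 + R² − 2rR). The simulation is a Day 28 ANCOVA with 4 of 40 missing, 8 versus 8, and 4,000–5,000 trials per setting.

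| R | r | Formula | Simulated |
|---|---|---|---|
| 1 | 0.3 | 0.826 | 0.824 |
| 1 | 0.5 | 0.888 | 0.885 |
| 1 | 0.7 | 0.945 | 0.943 |
| 1 | 0.9 | 0.999 | 0.998 |
| 1.25 | 0.5 | 0.969 | 0.966 |
| 1.25 | 0.7 | 1.015 | 1.014 |
| 1.25 | 0.8 | 1.025 | 1.023 |
| 1.5 | 0.5 | 1.006 | 1.003 |
| 1.5 | 0.67 | 1.025 | 1.025 |
| 1.5 | 0.8 | 1.001 | 0.998 |

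The slope is rR, and the worst case is rR = 1. Setting the ratio to 1 gives break-even correlations of 0.90, 0.76, 0.62 and 0.47 at R = 1, 1.1, 1.25 and 1.5; adjustment pays below these. A smaller simulation of the MMRM itself (unstructured covariance, t with 30–32 df standing in for Kenward-Roger) gave 0.886, 0.942 and 0.998 at R = 1 with r = 0.5, 0.7 and 0.9, and 1.020 at R = 1.5 with r = 0.67.

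**4. Stratum.** Added to baseline, it narrows the interval by a further 1–2% if the strata differ by 0.3 baseline SD and by 4–5% if they differ by 0.5 SD. If it is not prognostic, it widens the interval by 0.6% (0.8% with a 20:80 split).

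**5. Missingness that depends on baseline.** Assume 10% missing, with log-odds of 1 per baseline SD in one arm only. The unadjusted difference is then off by 0.010–0.048 SD for dropout before Day 7 and by 0.004–0.017 SD if only Day 28 is missing (r from 0.9 down to 0.5). With baseline in the model it is about 0. For scale, at r = 0.5 and R = 1 the change SD is 1, so the standard error for 8 versus 8 is √(2/8) = 0.5 SD.

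**6. Baseline drift between the parts.** The 300 mg arm lies wholly in the first part and the 100 mg arm wholly in the second, while placebo is half in each. A drift of 0.5 SD therefore shifts those contrasts by 0.5 × 0.5 × (1 − r) in absolute size: 0.125, 0.075 and 0.025 SD at r = 0.5, 0.7 and 0.9. Simulated shifts of about ±0.13 SD at r = 0.5 fell to about 0 after adjustment. The 500 mg contrast is protected, because its ratio to placebo is 2:1 in both parts.

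**7. Slopes that rise with dose.** Assume slopes 0.8/1.0/1.2/1.4 (placebo/100/300/500 mg) and residual SD 0.6, so the change slopes are −0.2/0/0.2/0.4.

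- The pooled change slope is (8×(−0.2) + 8×0 + 8×0.2 + 16×0.4)/40 = 0.16, pulled towards the largest arm.
- The placebo variance rises from 0.36 + 0.2² = 0.400 to 0.36 + 0.36² = 0.490. The 100 mg variance rises from 0.360 to 0.386.
- For 100 mg versus placebo the sampling SD ratio is √(0.875/0.760) = 1.07 before the cost of estimating the terms. Simulation gave 1.10 for 100 mg and 1.05 for 500 mg, with intervals 1.5% narrower.
- The model pools the variance (0.414 on average), which understates the placebo variance. Simulated 500 mg coverage fell from 94.6% to 92.6%.

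Across the settings tried, the sampling SD rose by about 5–14% and 500 mg coverage was about 92.5–93.5%.

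**The case against.** The strongest reply is that the planned model is valid as it stands and that the gain may not exist. The entry cap of antigenic AAT below 8 µM (protocol 8.1) may compress the baseline SD and so raise R, where the table runs from a small gain to a small loss. At R = 1 and r = 0.7 adjustment is worth 1/0.943² = 1.125, about 12% more subjects; at R = 1.25 and the same correlation it loses about 3% (1/1.014² = 0.97). If the drug effect grows with baseline, slopes differ by arm, and step 7 shows that a narrower interval need not mean a better estimate. Nothing in the documents says that ppFEV₁ predicts AAT. All of this stands. It is why the gain is stated as possible and why the unadjusted model should be kept.

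Text after the model in protocol 12.3.3.1 is redacted and might hold an adjusted supportive analysis. That would not change the primary model, which the SAP lists in full.

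A reader might go further and infer that the omission biases the primary result or inflates type I error. The documents do not support that. With complete data and no drift the difference is unbiased, and leaving out a prognostic stratum makes intervals conservative. Nor is the sample-size statement undermined: SAP 7.2 targets the absolute Day 28 level at 500 mg, not these contrasts. The protocol and SAP do not conflict on the model either.

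**Conclusion.** The omission is real in both models and both documents. It is an opportunity for improvement, not an error. The 2.5% limit on the loss (2.7% with a 20:80 stratum split) holds only for a slope common to all arms; where slopes rise with dose, the loss in true precision can be larger and coverage somewhat low.

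The possible biases are small beside a standard error near 0.5 SD: at most about 0.05 SD from baseline-dependent missingness and about 0.13 SD from an assumed 0.5 SD drift, the latter in the 100 mg and 300 mg contrasts only. Drift not carried by baseline is a separate issue that this change does not settle.

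Every SD, correlation, slope, stratum effect, missingness mechanism and drift used here is an assumption. Confidence that adjustment will help in this trial is moderate.

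**What to change.** - In SAP 9.3.1.2, add baseline functional AAT (continuous), its interaction with visit, and the ppFEV₁ stratum as fixed effects. In SAP 9.3.2.2, do the same with baseline antigenic AAT.
- Name these terms as the covariates in the missing-at-random sentence.
- Keep the planned unadjusted MMRM as a sensitivity analysis; it also covers slopes that differ by arm.
- Align protocol 12.3.3.1 and 12.3.3.3.
- Make the change before database lock and before any unblinded look at AAT data. Protocol 10.7.1 and 12.3.5.1 and SAP 10.1 allow an unblinded sponsor team to look at any time, so lock alone is too late a safeguard.

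**Cost.** No new data are needed. The model gains four parameters (baseline 1, baseline-by-visit 2, stratum 1) and uses about two of the 32 degrees of freedom at Day 28. The SAP change needs an approved amendment (SAP 4). The protocol change needs approval by the investigator and the sponsor and submission to regulators, and ethics committee notification if it is judged to affect scientific quality significantly (protocol 13.2.4).
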